3.5 Study Timeline

Month 1-8:

(1) Analyze existing practice patterns focused on 6 decision points derived from the NCCN decision tree for NSCLC (see Main Scientific Question). The study of practice patterns will be based on direct observation of new patient visits coded by a trained research coordinator and review of medical records.

(2) Programming of NSCLC decision aid by a research fellow under my direction, conducted with technical assistance as needed from PwP. The results will be reviewed by co-investigators for accuracy and ease of use.

Month 8-20: Conduct prospective trial of the decision aid.

Month 21-27: Completion of data collection and data analysis activities.

First Participant in (estimated date of first participant enrolled): from 6/1/2014 to 2/23/2015

Last Participant in (estimated date of last participant enrolled): from 5/31/2015 to 8/1/2015

Last Participant Last Visit (estimated date of completion of Therapy for all participants enrolled): from 5/31/2015 to 8/1/2015

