6.2 Determination of Sample Size and Accrual Rate

6.2.1 Sample Size and Power Estimate

We expect that the clinical volume of 30 patients/month for 12 months will yield a potential enrollment pool of 360 patients. Anticipating a 30% decline, dropout, or ineligibility rate at the time of potential enrollment, then at least 250 patients should be evaluable. The sample size was determined based on the primary outcomes of changes in practice patterns. For each disease stage, a test of at least a 25% improvement using the decision aid compared with the pre-intervention results in the proportion of patients satisfying the stage-specific criterion listed above will be carried out (see Primary Endpoint for practice pattern metrics). In addition, the entire study sample will be evaluated to test for a change in smoking cessation plans. Patients will be included in up to 3 individual analyses. The maximum sample size for any one test is based upon assuming a null hypothesis of 50% in the pre-intervention cohort. This estimate for the null hypothesis will be modified using the results obtained prior to use of the decision aid (Months 1-8). Based upon the one-sample binary exact test with power set at 90% and a 2-sided type I error of 0.017 (adjusted for up to 3 tests for all patients), 53 patients would be required for each test. The test would reflect the actual accrual by stage with the use of the decision aid. With a fixed type I error of 0.017, this means for any individual test that the sample size may differ from 53, and the null hypothesis may differ from 50% and result in reduced power but will be at least 80%. For example, if adjuvant chemotherapy is given after surgery to 40% of stage IB and II patients determined from the pre-intervention assessment, then a test to detect a 50% improvement to 60% will require 70 patients with 80% power and 88 patients with 91% power. Similarly, if 60% of patients satisfy the smoking cessation criterion during the

pre-intervention interval, a 50% improvement will require 32 patients with 92% power, but a 15% improvement with 90% power requires 135 patients across all disease stages. It is therefore not anticipated that the comparisons will require more than the expected enrollment of 250 patients.

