6.2.2 Accrual estimates

The total number of participants to be enrolled is 250. The expected number of participants to be enrolled per quarter is 60-65

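### The enrolment dates in section 3.5 are ambiguous; on their likelier reading accrual lasts 5.2 months and yields about 104-113 patients, not the 250 expected in 3.1 and 6.2

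*Combined protocol and SAP*

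**What the plan says.** Section 3.5 lists the milestones as "First Participant in (estimated date of first participant enrolled): from 6/1/2014 to 2/23/2015" and "Last Participant in (estimated date of last participant enrolled): from 5/31/2015 to 8/1/2015". The last visit of the last participant carries the same pair of dates as the last enrolment. The same section also keeps the schedule in study months: "Month 8-20: Conduct prospective trial of the decision aid", which is 12 months.

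Section 6.2.1 builds the enrolment figure on 12 months: "We expect that the clinical volume of 30 patients/month for 12 months will yield a potential enrollment pool of 360 patients". It then allows for losses ("Anticipating a 30% decline, dropout, or ineligibility rate at the time of potential enrollment") and arrives at 250 evaluable patients. Section 6.2.2, like section 3.1, states "The total number of participants to be enrolled is 250" and "The expected number of participants to be enrolled per quarter is 60-65".

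The tests in 6.2.1 are sized one by one: "Based upon the one-sample binary exact test with power set at 90% and a 2-sided type I error of 0.017", with 53 patients per test for a null of 50%, and worked examples of 70, 88, 32 and 135 patients. The section allows a test to have a different size or null, with reduced power, but says power will be at least 80%. It closes by concluding that no comparison should need more than the expected 250.

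**The concern.** Two calendars seem to stand side by side. The first date of each pair fits a 12-month accrual period. The second dates, taken together, leave less than half of that. If the dates were revised and the enrolment figures were not, the plan promises a number of patients that its own rate cannot supply in the time given.

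At stake is the last step of 6.2.1, that enrolment is large enough for every comparison, and with it the 80% power floor for the primary practice-pattern tests. Those tests, apart from smoking cessation, draw on separate stage groups, so a shortfall in the total is divided among them.

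**Working it through.** **Inputs.** Dates and Month 8-20: section 3.5. Clinic volume of 30 per month, 12 months, 30% loss, exact one-sample binomial test, two-sided 0.017, and all per-test sizes: 6.2.1. Rate of 60-65 per quarter and total of 250: 3.1 and 6.2.2. A month is taken as 30.4375 days.

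**1. The plan's enrolment figure.** 30 × 12 × (1 − 0.30) = 252, and 4 quarters × 60-65 = 240-260. Both agree with 250.

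**2. The plan's power figures.** Exact binomial, 0.017 / 2 = 0.0085 per tail:

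| Patients | Null to alternative | Stated power | Recomputed |
|---|---|---|---|
| 53 | 50% to 75% | 0.90 | 0.908 |
| 70 | 40% to 60% | 0.80 | 0.804 |
| 88 | 40% to 60% | 0.91 | 0.914 |
| 32 | 60% to 90% | 0.92 | 0.906 |
| 135 | 60% to 75% | 0.90 | 0.908 |

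All agree within two points, if the 25% (53 patients) and 15% (135 patients) improvements are read as percentage points. None of these calculations uses 250.

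**3. Accrual windows that the dates permit.** Months = days / 30.4375; patients = months / 3 × 60-65.

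| Reading | Window | Days | Months | Patients |
|---|---|---|---|---|
| First date of each pair | 6/1/2014 to 5/31/2015 | 364 | 11.96 | 239-259 |
| Second date of each pair | 2/23/2015 to 8/1/2015 | 159 | 5.22 | 104-113 |
| Ranges, longest | 6/1/2014 to 8/1/2015 | 426 | 14.0 | 280-303 |
| Ranges, shortest | 2/23/2015 to 5/31/2015 | 97 | 3.19 | 64-69 |

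On the second dates, 21 per month (30 less 30%) gives 21 × 5.22 = 110, inside the same range. The whole clinic volume with no losses gives 30 × 5.22 = 157. Reaching 250 would need 250 / 5.22 = 48 per month, above the stated volume of 30.

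**4. Smoking test on the second dates.** This test uses all patients. For 60% to 75%, power is 0.788 with 104 patients, 0.812 with 110 and 0.823 with 113, against 0.908 with 135. Exact power moves in steps; over all sizes from 104 to 113 it lies between 0.77 and 0.84.

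**5. Stage tests on the second dates.** In the base case (50% to 75%), power is 0.777 with 38 patients, 0.747 with 39 and 0.821 with 40. No smaller size from 30 up reaches 0.80, so 40 is the least that meets the floor. The four stage groups (IB-IIB with surgery, III with surgery, III without surgery, IV) do not overlap. Three groups of 40 need 3 × 40 = 120, more than 113. So at most two of the four can reach 80%, however patients are spread. With 250, four groups of 53 need 4 × 53 = 212, which is possible, though not assured.

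**The case against.** The strongest reply is that section 3.5 does not set a 5.2-month window. Each pair is labelled an estimate, nothing says the second date replaces the first, and Month 8-20 still stands in the same section. Two of the four windows above accommodate 250. This stands: a reader might infer that 250 cannot be delivered under the plan, but the documents support that only if the second dates are current.

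That reading is still the likelier one. Each line describes a single estimated date; the first dates reproduce the planned 12 months almost to the day; and as a range, the first enrolment alone would be uncertain by almost nine months. Section 3.5 shows another sign of partial updating: it puts completion and analysis in Month 21-27, while the abstract has Month 20-24 and 3.5.1 allows four months after accrual closes.

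A reader might also infer that 250 lies behind every power statement. It does not. The sizes are per test, they reproduce whatever the dates, and only the 135-patient example exceeds 104-113 outright. Even there 6.2.1 tolerates lower power down to 80%, and the recomputed values fall on both sides of that floor. What rests on 250 is the conclusion that enrolment covers the tests.

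Finally, the documents give no stage mix, so the power of any one stage test on the short window cannot be stated, and part of the risk exists even at 250 (only 250 − 212 = 38 to spare). This too stands. The two-of-four limit does not depend on the mix, but it does depend on the base case: another observed null or improvement changes the 40.

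**Conclusion.** The point holds as an unresolved inconsistency with a conditional consequence. As written, section 3.5 does not establish the 12 months of accrual that 6.2.1 needs, because its dates permit anything from 3.2 to 14.0 months (64-303 patients).

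If the second dates are current, the window contradicts Month 8-20 in the same section and the 250 in 3.1, 6.2.1 and 6.2.2, and 250 is out of reach even from the full clinic volume. The 90% power for the smoking example then falls to about 0.79-0.82, and the 80% floor cannot hold in the base case for at least two of the four stage groups. These results assume the plan's own accrual rate, its exact test at two-sided 0.017, and improvements in percentage points. If 12 months is still intended, the enrolment figures stand and only the dates are wrong.

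**What to change.** State in section 3.5 which dates are current, and whether each pair is a revision or a range. Reconcile them with Month 8-20, the 60-65 per quarter and the total of 250.

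- If the 5.2-month window stands: restate expected enrolment (about 104-113) in 3.1, 6.2.1 and 6.2.2, give the power of each test at the size then expected, with the stage mix assumed, and withdraw the 80% floor for any test that does not meet it.
- If 12 months of accrual is still intended: correct the dates in 3.5.

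Either way the change is to protocol wording, made by amendment under section 7.4. The downside of the first option is that the stated enrolment and power become less favourable.

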3.5.1 Study Completion

Completion of data collection and data analysis activities will be completed within 4 months after the study is closed to accrual.

4 Study Procedures and Observations

4.1 Schedule of Procedures and Observations

4.1.1 Pre-consultation Assessments

The pre-consultation questionnaires will take about 20-30 minutes to complete.

- Decision Support Preference Questionnaire (DMPQ)
- FACT-L
- NCCN-Functional Assessment of Cancer Therapy Lung Symptom Index-17 (NFLSI-17).
- Decisional Conflict Scale (DCS): The DCS will be completed before and after the patient's PwP training session.

4.1.2 Patients with Power Training

The patient will be trained on the use of the Patients with Power software by the Clinical Research Coordinator. The training will take approximately 15 minutes.

4.1.3 Post-consultation Assessments

The post-consultation questionnaires, completed by the patient and their oncologist, will take about 10-20 minutes to complete.

- Decisional Conflict Scale (DCS): The DCS will be also be completed before the patient's PwP training session.
- Post-Consultation Questionnaire
- Satisfaction with Health Care Decision (SWD).

Procedure	Clinical Visit
Informed consent	X
Decision Support Preference Questionnaire (DMPQ)	X ¹
FACT-L Questionnaire	X ¹
FACT/NCCN-Lung Symptom Index (NCCN-FACT FLSI-17) Questionnaire	X ¹
Decisional Conflict Scale (DCS) Questionnaire	X ^{1,2}
PwP Training Session	X
Post-Consultation Questionnaire	X ²
Satisfaction with Health Care Decision (SWD) Questionnaire	X ²

¹pre consultation questionnaire

²post consultation questionnaire

5 Reporting and Documentation of Results

5.1 Evaluation of PwP

1. **Decision Support Preference Questionnaire (DMPQ):** The Decision Support Preference Questionnaire (DMPQ) is a brief assessment of patients' preferred style in decision making with their physician. Patients check off the single statement out of five that best describes their preferred level of shared decision making responsibility. The Decision Support Preference Questionnaire (DMPQ) will be completed *once before the consultation*.
2. **FACT-L:** The FACT-L is a 44-item self-report instrument that measures multidimensional quality of life, focused on common concerns of lung cancer patients measured on a 5-point Likert scale. It includes domains of Physical Well Being, Emotional Well Being, Social Well Being, and Functional Well Being. Available in eight languages, it is currently being used in several Phase II and III lung cancer clinical trials (Cella DF, Bonomi AE, Lloyd SR, Tulsky DS, Kaplan E, Bonomi P. Reliability and validity of the Functional Assessment of Cancer Therapy-Lung (FACT-L) quality of life instrument. Lung Cancer. 1995 Jun;12(3):199-220). The FACT-L will be completed *once before the consultation*.
3. **NCCN-Functional Assessment of Cancer Therapy Lung Symptom Index-17 (NFLSI-17):** The NCCN-FACT FLSI-17 is a 17-item patient-reported questionnaire that indexes the symptoms most highly valued by physicians, nurses, and patients with advanced-stage lung cancer.²⁵ It employs a five-point Likert scale and is scored from 0-68. It includes three subscales, Disease-Related Subscale (DRS), Treatment Side Effects (TSE), and Functional Well-Being (FWB). A unique aspect of this instrument is the

separation of disease-related and treatment-related effects. The NFLSI-17 will be completed *once before the consultation*.

4. **Decisional Conflict Scale**: The Decisional Conflict Scale (DCS) is a scale designed to measure patients' uncertainty in making health-related decisions, factors contributing to uncertainty, and patients' perceived effective decision-support. The DCS has 16 items and uses a five-point Likert scale. The scale is especially designed to help provide information about the efficacy of decision aids.²² It has been used in a variety of cancer prevention and treatment-related settings. The DCS will be completed *before and after the consultation*.
5. **Post-Consultation Questionnaire**: The Post-Consultation Questionnaire will be completed by the patient and their oncologist *once after the consultation*. It includes the following components:
 - a. Treatment Recommendations and Decisions: Treatments discussed, recommended, and chosen by the patient and their oncologist will be recorded. Options may include surgery, radiation therapy, chemotherapy, targeted therapy, observation, hospice, no treatment, or unresolved. The oncologist and patient will also be asked for an estimation of the tolerance of the treatment. This information will be obtained from the patient and oncologist *immediately after the consultation*.
 - b. Prognosis Estimates: Estimates of prognosis with no treatment and with the recommended treatment will be obtained from the patient and oncologist *immediately after the consultation*.
 - c. Program Evaluation: The patient will be asked to score the extent to which this process increased their understanding of their cancer treatment options and confidence in their oncologist *immediately after the consultation*.
6. **Satisfaction with Health Care Decision (SWD)**: Although the DCS will provide a general measure of satisfaction with the medical encounter, it does not specifically query the patient's satisfaction with the health care decision itself. The Patient Satisfaction with Health Care Decision (SWD) is a six-item scale with excellent reliability and good discriminant validity. The instrument was validated using a sample of postmenopausal women specifically to evaluate the utility of patient decision aids.¹⁴ The strength of the SWD is that it measures satisfaction with the decision made regardless of how good or bad the prognosis or health outcome might be for the individual patient. The SWD will be completed *once after the consultation*.

7. Acceptability: The PwP website will be monitored for usage *during the consultation and afterwards*. Patients will be given an account to enable continuous, unlimited access for the life of the grant. Usage statistics will be monitored only in aggregate terms, without reference to specific content accessed by individual patients. Repeat visiting to the website will be quantified to establish evidence of acceptance on the part of patients. Physician acceptance will be judged by rates of participation in using the decision aid during the consultation process.

6 Statistical Considerations and Evaluation of Results

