Duration of study	
Twenty four months:
 
Month 1-8: (1) Analyze existing practice patterns focused on 6 decision nodes derived from the NCCN decision tree for NSCLC. The study of practice patterns will be based on primarily on review of medical records by a trained research coordinator under [name] direction. (2) Programming of NSCLC decision aid under [name] direction, conducted with technical assistance as needed from PwP. The results will be reviewed by co-investigators for accuracy and ease of use.
 
Month 8-20: Conduct prospective trial of the decision aid, collecting data directly from patients over the course of their initial 2 consultations.
 
Month 20-24: Completion of data collection and data analysis activities.

Study Intervention	The interactive PwP interface allows structured exploration of choices, sequencing, and timing of therapies. The aid thus enables the patient to discuss proposed treatments with the oncologist (rather than assuming passive acceptance). Furthermore, the decision aid allows evolving display of the treatment choices and timeline/calendar in a graphical, simplified format during the discussion (rather than assuming absorption and recall of details of a verbal communication). We will collect pilot data related to the collaborative, patient-oriented approach facilitated by this decision aid.
Study Assessments	
A total of five patient-reported instruments will be used to score overall and lung cancer-specific quality of life, decision-support preferences, decisional conflict, and satisfaction with decision:
 
 1. Decision Support Preference Questionnaire (DMPQ) 2. FACT-L 3. FACT/NCCN-Lung Symptom Index (NCCN-FACT FLSI-17) 4. Decisional Conflict Scale (DCS) 5. Post-Consultation Questionnaire 6. Satisfaction with Health Care Decision (SWD)

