1.2.1 Patients' Reactions to PwP Proof of Concept

The PwP prototype decision aid has met with very positive responses in the breast cancer community:

From a newly diagnosed patient: “[I]t is amazing. It seems that my surgeon is following the right course. She has not talked about chemotherapy yet since the surgery comes first and then pathology.... My surgeon is also interested in learning more about this software.”

From a 2-year survivor: “[K]nowing the NCCN guidelines as compared to what doctors are recommending is really valuable.”

[figure not shown]
From a 6-year survivor: “I love the concept and the sleek, clean, bright design.... With your drop down lists, it was a snap to pick the correct answers. Your site has the potential to be a great source of information for hungry patients. I would have loved to have had something like it when I went through treatment.”

From a friend of a patient: “She and I went on[line] together. She is not tech savvy so I wasn't sure how she would react. I am a geek so it makes perfect sense to me. She really liked it and was able to navigate around with ease.... We especially liked the fact that information was available at decision points where choices would need to be made. That makes the journey a whole lot less confusing.”

From a cancer survivor and activist: “If this existed when I'd been diagnosed, it would've been the compass to help guide and map out my journey.”

Startup technology companies often launch prototypes in high-profile diseases such as breast cancer. This project will extend the innovation to a more marginalized and underserved population in NSCLC. While extending the concept to NSCLC, our project will preserve the core features of the decision aid, including the graphical visualization of the guidelines, the ease of navigation in the user interface, the personalization enabled by the drop-down boxes, and the ability to create, modify, and review multiple scenarios (see Figure 1).

Figure 1. Screenshot of Patients with Power decision aid, designed currently for patients with breast cancer.

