1.3 Rationale for the Proposed Study

This is a two-year career development project to develop and field-test a decision aid based on the NCCN patient guidelines for NSCLC. The study goal is to improve the treatment decision-support process in NSCLC patients in an academic medical center. If successful, this decision aid will be disseminated more broadly to community settings.

This study will consist of a development phase followed by an evaluation phase. After initial prototyping, refinement, coding, and implementation of the intervention, a study will be implemented using a pre/post design to estimate the effect size of the intervention with respect to disseminating NCCN-guided treatment choices (primary outcome) and to generate preliminary data about secondary outcomes.

Specifically, this project will:

1. Characterize physician and patient populations and treatment decisions in the UCSF thoracic oncology practices.
2. Establish the acceptability, feasibility, and effectiveness of a novel decision aid for decisions made about treatment for NSCLC.

3. Conduct an evaluation of changes in NCCN-guided practice patterns before and after implementation of the decision aid, with respect to 6 clinical scenarios:

1. All patients: if smoking cessation intervention is provided at initial visit;
2. Stage IB-IIB patients receiving surgery: if adjuvant chemotherapy is given after surgery;
3. Stage III patients receiving surgery: if pathologic staging of mediastinal nodal disease is done prior to initiation of therapies;
4. Stage III patients not receiving surgery: if pathologic staging of mediastinal nodal disease is done prior to initiation of therapies
5. Stage III patients not receiving surgery: if concurrent chemoradiation is given upfront;
6. Stage IV patients: if molecular testing is done prior to initiation of systemic therapy.

4. Collect data to facilitate the design of future larger-scale evaluations, including assessments of physician-patient agreement and patients' levels of decisional conflict and satisfaction with decisions made.

2 Objectives of the Study

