6.1 Study Endpoints

Primary Endpoints: The practice pattern survey completed during the first 8 months will provide the baseline data that will be compared to results obtained after implementation of the decision aid.

Secondary Endpoints: A total of five patient-reported instruments will be used to score overall and lung cancer-specific quality of life, decision-support preferences, decisional conflict, and satisfaction with decision:

Decision Support Preference Questionnaire (DMPQ)

FACT-L

FACT/NCCN-Lung Symptom Index (NCCN-FACT FLSI-17)

Decisional Conflict Scale (DCS)

Post-Consultation Questionnaire

Satisfaction with Health Care Decision (SWD).

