6.1.1 Study Design

This study involves the evaluation of the decision support tool Patients with Power, previously used with breast cancer patients, in the non-small cell lung cancer patient population.

1. Characterize physician and patient populations and treatment decisions in the UCSF thoracic oncology practices.
2. Establish the acceptability, feasibility, and effectiveness of a novel decision aid for decisions made about treatment for NSCLC.
3. Conduct an evaluation of changes in NCCN-guided practice patterns before and after implementation of the decision aid, with respect to 6 clinical scenarios:

All patients: if smoking cessation intervention is provided at initial visit;

Stage IB-IIB patients receiving surgery: if adjuvant chemotherapy is given after surgery;

Stage III patients receiving surgery: if pathologic staging of mediastinal nodal disease is done prior to initiation of therapies;

Stage III patients not receiving surgery: if pathologic staging of mediastinal nodal disease is done prior to initiation of therapies;

Stage III patients not receiving surgery: if concurrent chemoradiation is given upfront;

Stage IV patients: if molecular testing is done prior to initiation of systemic therapy.

4. Collect data to facilitate the design of future larger-scale evaluations, including assessments of physician-patient agreement and patients' levels of decisional conflict and satisfaction with decisions made as well as potential correlations to patient-reported quality to life.

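### The patient's Program Evaluation rating (5.1, item 5c), as described, asks only about an increase, so a fall would look like no change; the score also describes the whole process, not the aid

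*Combined protocol and SAP*

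**What the plan says.** The rating is component c of the Post-Consultation Questionnaire, listed under "5.1 Evaluation of PwP". The patient is to "score the extent to which this process increased their understanding of their cancer treatment options and confidence in their oncologist", and the timing is "immediately after the consultation". No matching question is asked beforehand. The process being rated is not defined. By Sections 4.1.2 and 5.1 it can include the coordinator's training session, use of the website and the consultation itself.

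One of the project's aims, stated in Sections 1.3 and 6.1.1, is to "Establish the acceptability, feasibility, and effectiveness of a novel decision aid". Patient-reported data come only from the decision-aid phase, which the synopsis (Duration of study) describes as "Conduct prospective trial of the decision aid, collecting data directly from patients over the course of their initial 2 consultations". The pre-intervention phase supplies practice patterns only: "The practice pattern survey completed during the first 8 months will provide the baseline data" (Section 6.1).

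None of the six secondary objectives in Section 2.2 names this rating. Section 6.3.2 plans correlations and a comparison of patient and physician reports, but gives no hypothesis, test or threshold for it.

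**The concern.** A question about the size of an increase takes the direction for granted. As described, its lowest answer is no increase, and a patient who came away less sure of the oncologist has nowhere to say so.

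This matters most for confidence. The aid lets patients set the guideline beside what they are being told, and one survivor quoted in Section 1.2.1 says that knowing "the NCCN guidelines as compared to what doctors are recommending is really valuable". Such a comparison could lower confidence in the oncologist as well as raise it. Neither the FACT-L nor the Decisional Conflict Scale, as printed in the appendix, has an item on confidence in the oncologist. The Satisfaction with Decision scale is described as addressing the decision. Among the patient measures described, item 5c is the only one directed at this question.

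The second difficulty is attribution. A consultation about treatment options can be expected to improve understanding with or without a website, and no group rates a consultation without the aid. A good score therefore says little about what the aid added.

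**Working it through.** The documents state no figure for this rating, so there is nothing to reproduce. The check is in two parts.

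**Reading the passages together**

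- Direction: item 5c asks about an increase only.
- Timing: one rating, after the consultation, with no earlier value.
- Comparator: none. Patients are questioned only in the decision-aid phase, and the baseline phase holds practice patterns.
- Object: the process as a whole, although the section heading names the aid.

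**Size of the lean, on stated assumptions**

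Inputs: n = 250 (Section 3.1). The scale and the distributions below are assumed, because the documents give neither.

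Let D be a patient's true change. An increase-only score records max(D, 0). Then

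recorded mean − true mean = (proportion who decreased) × (average size of their decrease).

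The lean is never negative, and it is zero only if nobody decreases.

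*Illustration 1: 0 to 4 scale, changes of +2, 0 or −2.*

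- 30% up, 30% down, 40% unchanged. True mean = 2 × 0.30 − 2 × 0.30 = 0. Recorded mean = 2 × 0.30 = 0.60. SD = 2 × √(0.30 × 0.70) = 0.917. SE = 0.917/√250 = 0.058. 95% CI = 0.60 ± 1.96 × 0.058 = 0.49 to 0.71. Recorded as decreased: 0%.
- 10% up, 10% down, 80% unchanged. True mean = 0. Recorded mean = 2 × 0.10 = 0.20. SD = 2 × √(0.10 × 0.90) = 0.60. SE = 0.60/√250 = 0.038. 95% CI = 0.13 to 0.27. Recorded as decreased: 0%.

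*Illustration 2: true change normal with mean μ and SD 1, floored at 0.* With Φ and φ the standard normal distribution and density functions, the recorded mean is m = μΦ(μ) + φ(μ). The recorded variance is (μ² + 1)Φ(μ) + μφ(μ) − m². For the increase-only score z = m/SD × √250; for a two-way score z = μ × √250.

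| True mean μ | Recorded mean | Recorded SD | z, increase-only | z, two-way |
|---|---|---|---|---|
| 0 | 0.40 | 0.58 | 10.8 | 0 |
| −0.25 | 0.29 | 0.50 | 9.1 | −4.0 |
| −0.5 | 0.20 | 0.41 | 7.6 | −7.9 |
| −1 | 0.08 | 0.26 | 5.0 | −15.8 |

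Judged by whether the mean exceeds zero, the increase-only score looks positive even when patients on average got worse.

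*Same model, another criterion: more than half of the 250 report any increase.* The probability is P(X > 125) with X binomial (250, Φ(μ)). It is 0.47 at μ = 0 and 0.0006 at μ = −0.25. What the lean does to a conclusion therefore depends on a criterion that the plan does not set.

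**The case against.** The strongest reply is that the form has not been seen. Item 5c is a one-sentence summary, and the appendix text available for review ends with the Decisional Conflict Scale. A reader might infer that the form cannot record a decrease. The documents do not support that as a fact: the form may, for example, ask for agreement with a statement and so have a disagree side, and it may already score understanding and confidence separately. This stands, and the point is therefore confined to the rating as described.

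A reader might also infer that a favourable result is almost certain. That needs a rule that any mean above zero is favourable, and the plan has none. In Illustration 1, 70% or 90% of patients report no increase, which many would call a poor result. This stands too.

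A third inference is that the study credits the score to the aid. The heading points that way, but the item asks about the process and no planned analysis assigns the score to the website. The aid is meant to be used within the consultation, so rating the combination is reasonable. The lack of a comparator is shared by all the patient-reported measures.

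Finally, other measures carry more weight. Section 5.1, item 7, judges patient acceptance by repeat website visits and physician acceptance by participation. The Decisional Conflict Scale is taken before and after and can worsen. The evidence in Section 1.2.1 is also mixed, since a newly diagnosed patient there sounds reassured about her surgeon's plan.

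What the reply does not remove is the one-directional wording, or the absence of another described measure aimed at confidence in the oncologist.

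**Conclusion.** The point holds as a low-weight improvement. As described, the rating would merge a decrease with no change and so lean upward, and without a baseline or comparator it cannot separate the aid from the consultation.

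The size is unknown. The illustrated lean is 0.20 to 0.60 on an assumed 0 to 4 scale, and it depends on how many patients get worse and by how much. The effect is limited to a descriptive patient rating. The primary endpoint, the secondary objectives and the sample size are untouched. The documents do not tie the acceptability aim or wider dissemination to this item, so it would go too far to say that either rests on it.

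The conclusion assumes that the form follows the wording of item 5c. If it already offers two-way answers, only the mismatch with Section 5.1 and the labelling of the result remain.

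**What to change.** In item 5c and on the form:

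- Use a two-way response: much decreased, decreased, no change, increased, much increased.
- Ask about understanding and about confidence as separate items.
- Report the proportion decreased as well as the proportion increased for each.
- Label the result as descriptive of training, aid and consultation combined, not as an effect of the aid. Rewording cannot supply the missing comparison group.

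The cost is a minor rewording of one study-specific form and a slightly longer questionnaire. No validated instrument changes. If the form already has two-way options, Section 5.1 need only be aligned with it.
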